5.2. Analysis of primary immunogenicity endpoint

The Primary immunogenicity objective is to evaluate the serum IgG GMCs to the 10 serotypes in PNEUMOSIL, alone and in comparison to IgG antibody responses to these serotypes induced by Prevenar 13 and Synflorix, at 4 weeks post booster dose. For each serotype, two-sided 95% CIs for the within-group GMC and the between-group GMC ratios will be calculated. Differences between groups will be considered statistically significant if the 95% CI for the GMC ratio excludes 1.0.

5.3. Analysis of Secondary Immunogenicity Endpoints

5.3.1. Secondary Objective 1: functional antibody responses at 4 weeks post booster

Secondary objective 1 is to evaluate the functional serum antibody responses (GMTs) to the 10 serotypes in PNEUMOSIL, alone and in comparison to the responses to these serotypes induced by Prevenar 13 and Synflorix, at 4 weeks post booster dose. This analysis will be done among a subset of 50 subjects per group (see Section 3.5). For each serotype, two-sided 95% CIs for the within-group GMT and the between-group GMT ratios will be calculated. Differences between groups will be considered statistically significant if the 95% CI for the GMT ratio excludes 1.0.

5.3.2. Secondary Objective 2: IgG seroresponse rates 4 weeks post booster

Secondary objective 2 is to assess seroresponse rates (IgG antibody levels and functional responses) to the 10 serotypes in PNEUMOSIL, alone and in comparison to seroresponse rates for these serotypes induced by Prevenar 13 and Synflorix, at 4 weeks post booster dose (functional responses assessed in a subset of 50 subjects per group). For each serotype, the proportion of responders (IgG concentrations $\geq 0.35 \mu\text{g/mL}$; IgG concentrations $\geq 1.0 \mu\text{g/mL}$; and OPA titers ≥ 8) at 4 weeks post booster will be reported, together with 95% CIs for the proportions and for differences between the PNEUMOSIL and comparison groups. Differences between groups will be considered statistically significant if the 95% CI excludes 0.0.

5.3.3. Secondary Objective 3: IgG antibody responses 4 weeks post primary

Secondary objective 3 is to evaluate the serum IgG antibody responses (seroresponse rates and GMCs) to the 10 serotypes in PNEUMOSIL, alone and in comparison to antibody responses to these serotypes induced by Prevenar 13 and Synflorix, at 4 weeks post completion of primary vaccination. For each serotype, the proportion of IgG antibody responders (IgG concentrations $\geq 0.35 \mu\text{g/mL}$ and IgG concentrations $\geq 1.0 \mu\text{g/mL}$) and the GMC at 4 weeks post primary series will be reported, together with 95% CIs for the proportions and GMCs. Differences in seroresponse rates and GMC ratios (PNEUMOSIL versus each comparison group) will also be reported with 95% CIs. Differences between groups will be considered statistically significant if the 95% CI excludes 0.0 (for response rates) or 1.0 (for GMCs).

5.3.4. Secondary Objective 4: functional antibody responses 4 weeks post primary

Secondary objective 4 is to evaluate the functional serum antibody responses (seroresponse rates and GMTs) to the 10 serotypes in PNEUMOSIL, alone and in comparison to the functional antibody responses to these serotypes induced by Prevenar 13 and Synflorix, at 4 weeks post completion of primary vaccination in a subset of 50 subjects per group. For each serotype, the proportion of functional antibody responders (OPA titers ≥ 8) and the GMT at 4 weeks post

primary series will be reported, together with 95% CIs for the proportions and GMTs. Differences in response rates and GMT ratios (PNEUMOSIL versus each comparison group) will also be reported with 95% CIs. Differences between groups will be considered statistically significant if the 95% CI excludes 0.0 (for response rates) or 1.0 (for GMTs).

5.3.5. Secondary Objective 5: persistence of post-primary IgG responses

Secondary objective 5 is to evaluate the persistence of the post-primary serum IgG antibody responses (seroresponse rates and GMCs) to the 10 serotypes in PNEUMOSIL, alone and in comparison to IgG antibody responses to these serotypes induced by Prevenar 13 and Synflorix, at 9 months of age (prior to a booster dose). For each serotype, the proportion of IgG antibody responders (IgG concentrations $\geq 0.35 \mu\text{g/mL}$) and the GMC at V5 (just prior to booster) will be reported, together with 95% CIs for the proportions and GMCs. Differences in seroresponse rates and GMC ratios (PNEUMOSIL versus each comparison group) will also be reported with 95% CIs. Differences between groups will be considered statistically significant if the 95% CI excludes 0.0 (for response rates) or 1.0 (for GMCs).

5.3.6. Secondary Objective 6: persistence of post-primary functional antibody responses

Secondary objective 6 is to evaluate the persistence of post-primary functional serum antibody responses (seroresponse rates and GMTs) to the 10 serotypes in PNEUMOSIL, alone and in comparison to the functional antibody responses to these serotypes induced by Prevenar 13 and Synflorix, at 9 months of age, immediately prior to booster among a subset of 50 subjects per group. For each serotype, the proportion of functional antibody responders (OPA titers ≥ 8) and the GMTs at V5 (just prior to booster) will be reported, together with 95% CIs for the proportions and GMTs. Differences in response rates and GMT ratios (PNEUMOSIL versus each comparison group) will also be reported with 95% CIs. Differences between groups will be considered statistically significant if the 95% CI excludes 0.0 (for response rates) or 1.0 (for GMTs).

5.3.7. Secondary Objective 7: booster responses

Secondary objective 7 is to evaluate booster responses (serum antibody response GMCs and functional response GMTs) to PNEUMOSIL, alone and in comparison to booster responses to Prevenar 13 and Synflorix, from 4 weeks after completion of primary vaccination to 4 weeks after a booster dose (restricted to a subset of 50 subjects per group for functional responses). For each serotype and treatment group, the ratio of within-group GMCs and GMTs (V6 versus V4) will be reported, together with 95% CIs for these booster responses. The totality of the data (responses at V4, V6 and booster responses) will be descriptively compared between groups for clinical relevance.

In addition to tabulations of primary and secondary endpoints, immune response data will be summarized graphically at each of V4, V5, and V6, and over time using bar charts (OPA only) and reverse cumulative distribution (RCD) curves.

Due to the impact of the COVID-19 pandemic on clinic visit schedules, not all subjects selected for the OPA analysis at V4 contributed data at V5 and V6. Per Section 3.5, subjects not contributing V5 and V6 data were replaced with new subjects from the same field site and treatment group. To assess the robustness of Secondary Objective 7 results, the analysis of this objective will be repeated when restricting the sample to subjects who contributed both V4 and V6 data. The results of this sensitivity analysis and any related exploratory analyses will be only used to guide interpretation of the primary analysis results.

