Secondary Objective 5 is to evaluate the persistence of serum IgG antibody responses to the 10 serotypes in PNEUMOSIL at 9-18 months of age, prior to the booster dose. The percentage of responders (IgG $0.35 \mu\text{g/mL}$) and GMCs will be reported by PNEUMOSIL serotype and treatment group, together with 95% CIs. Serotype-specific differences in response rates (PNEUMOSIL vs. each comparator) and GMC ratios will be reported with 95% CIs.

Secondary Objective 6 is to evaluate – in a subset of subjects in the Primary PP_IMM Population – the persistence of functional antibody responses to the 10 serotypes in PNEUMOSIL as measured by OPA at 9-18 months of age, prior to the booster dose. The proportion of subjects with serotype-specific serum OPA titers $\geq 1:8$ and GMTs will be reported by PNEUMOSIL serotype and treatment group, together with 95% CIs. Serotype-specific differences in response percentages (PNEUMOSIL vs. each comparator) and GMT ratios will be reported with 95% CIs.

Secondary Objective 7 is to evaluate booster responses (serum IgG concentrations and functional responses) from 4 weeks after the primary series (V4) to 4 weeks post booster dose (V6). For each PNEUMOSIL serotype, the ratio of post-booster to post-primary series IgG GMCs and OPA GMTs will be reported by treatment group with 95% CIs, restricted to subjects who provide response data at both V4 and V6.

In addition to the summary measures of immunogenicity responses described above for each of the primary and secondary objectives, reverse cumulative IgG concentration and OPA titer distribution curves will be presented by serotype and treatment group.

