3.1. Visit Schedule and Evaluations

Study vaccinations will be scheduled to occur at 6 weeks of age (+2 week visit window; Visit 1 [V1]), 14 (+2) weeks of age (V3), and 9-18 (+1) months of age (V5). Standard Expanded Program on Immunization (EPI) vaccinations in The Gambia (except Prevenar 13) will be given concomitantly with each primary dose of study vaccine, at 10 (+2) weeks of age (V2), and at 9 months of age where reasonable (recognizing the impact of SARS-CoV-2 on the feasibility of clinic visits). Blood draws for immunogenicity assessments will occur 4 (+2) weeks after the second study vaccination (V4), immediately prior to booster vaccination (V5) at 9-18 months of age, and at 4 (+2) weeks after booster vaccination (V6), which serves as the end-of-study visit. All subjects with evaluable specimens will be assessed for serum IgG responses. For functional antibody responses, 50 subjects who completed V4 per protocol and intended to continue to V6

were selected from each treatment group for OPA specimen testing. Subjects who did not complete V5 or V6 per protocol were replaced with new subjects from the same field site and treatment group to contribute V5 and V6 OPA data (see Section 3.5). The study schema is presented in Table 1.

Table 1. Study Schema

Visit / Age (with length of visit window in parentheses)					
V1	V2	V3	V4	V5	V6
6 (+2) wks	10 (+2) wks	14 (+2) wks	V3+4 (+2) wks	9-18 (+1) mo	V5+4 (+2) wks
X, E	E	X, E	B	B, X, E	B

wks = weeks, mo = months, X = study vaccination, E= EPI vaccines, B = blood sample for immunogenicity testing

Solicited reactogenicity events (REs) and vital signs will be assessed at 30 (+/- 10) minutes following each study vaccination. Solicited local REs include tenderness, erythema/redness, and induration/swelling at the injection site. Solicited systemic REs include cutaneous rash, fever, irritability, drowsiness, and decreased appetite. In addition to in-clinic assessments on the day of vaccination, all subjects will be monitored by field workers for local and systemic reactogenicity events during the 6 days after each study vaccination administration.

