3.5. Selection of OPA Specimens

Prior to the interim analysis of primary series immunogenicity data, the PI provided the ratio of subject enrolments per field site expected to be achieved at the completion of the trial. Based on this ratio, the independent statistician selected (based on order of entry into the study, not randomly) the first 27 subjects with evaluable V4 specimens in each treatment group from the Brikama field site, and the first 23 subjects with evaluable V4 specimens in each treatment group from the Bundung site, such that a total of 50 subjects per group were selected for OPA analysis proportional to the enrolment total in each site. Selected subjects who did not complete V5 per protocol were later replaced with new subjects from the same field site and treatment group to contribute V5 and V6 OPA data (with replacements also selected in order of enrolment date, not randomly). If more than 10% of subjects fail to contribute evaluable results at a given visit, then additional subjects may have their specimens analysed to help ensure at least 45/group contribute to each secondary functional antibody analysis timepoint. The PATH Clinical Lead will make this determination in blind review of data once the availability of OPA results has been determined for all selected subjects.

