5. EVALUATION OF IMMUNOGENICITY

Analysis Populations: Primary and secondary immunogenicity will be evaluated within the Primary and Secondary Per Protocol Immunogenicity Populations, as noted in Table 3.

Data Sources: Primary immunogenicity objectives will be based on serotype-specific IgG antibody concentrations measured 4 weeks after the booster vaccination series (V6). Secondary objectives will be based on the serotype-specific IgG concentrations and OPA titers at three time points (4-weeks after completion of the primary series (V4), immediately prior to booster (V5), and V6).

Endpoint Definitions:

1. **GMC [or GMT]:** The geometric mean concentration (or titer) = antilog (mean $[\log_{10} x]$), where x is the assay result
2. **Response to study vaccine:**
 - IgG concentration $\geq 0.35 \mu\text{g/mL}$
 - IgG concentration $\geq 1.00 \mu\text{g/mL}$
 - OPA titer ≥ 8

5.1. General Comments on Reporting of Immunogenicity Objectives:

1. Differences in proportions of responders to each serotype in PNEUMOSIL will be reported as the PNEUMOSIL proportion minus the reference group (Synflorix or Prevenar 13) proportion, with 95% confidence intervals calculated using the Miettinen-Nurminen (1985) likelihood score method. If the response rate is 100% in each group, then two non-response records (one for each group) will be included and given a weight of 0.000001 to facilitate computation of the 95% CI. Differences in proportions will be considered statistically significant if the 95% CI excludes 0.
2. Within-group GMCs [GMTs] and 95% CIs for each serotype in PNEUMOSIL will be computed based on the antilog (base 10) of mean log10 concentrations [titers] and the corresponding CI limits for the mean log10 values, based on a log-normality assumption.
3. Between-group GMC [GMT] ratios will be reported as the PNEUMOSIL GMC [GMT] divided by the reference vaccine GMC [GMT]. 95% CIs for between-group GMC [GMT] ratios will be computed based on the antilog (base 10) of the corresponding CI limits for the difference in mean log10 concentrations [titers]. Differences between groups will be considered statistically significant if the 95% CI excludes 1.

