4. Within-group (booster response) GMC [GMT] ratios will be computed based on the antilog (base 10) of the mean within-subject differences in log10 concentrations [titers], V6 minus V4, restricted to subjects who contribute evaluable immunogenicity data at each time point. Confidence intervals for within-group GMC [GMT] ratios will be computed as in (3), and booster responses will be considered statistically significant if the CI excludes 1.0.

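### The SAP 5.3.7 robustness check for OPA replacement must return the same V6/V4 booster ratio as the main analysis, and Objective 7 has no between-group estimate with a CI

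*SAP*

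**What the plan says.** SAP 5.1 item 4 defines the booster ratio as the antilog of the mean within-subject log10 difference, V6 minus V4, "restricted to subjects who contribute evaluable immunogenicity data at each time point". Protocol 12.7.2 sets the same limit for Secondary Objective 7: "restricted to subjects who provide response data at both V4 and V6".

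OPA is tested in 50 subjects per arm, chosen at V4. SAP 3.1 reports that "Subjects who did not complete V5 or V6 per protocol were replaced with new subjects", and SAP 3.5 that "Selected subjects who did not complete V5 per protocol were later replaced with new subjects from the same field site and treatment group". Both sections say that the replacements supply V5 and V6 OPA data. To assess robustness to this replacement, SAP 5.3.7 states that "the analysis of this objective will be repeated when restricting the sample to subjects who contributed both V4 and V6 data", and that the result only guides interpretation of the main analysis.

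For the comparison between vaccines, 5.3.7 gives 95% CIs for the within-group ratios and then says: "The totality of the data (responses at V4, V6 and booster responses) will be descriptively compared between groups for clinical relevance". SAP 5.3.1 to 5.3.6, which cover Objectives 1 to 6, each plan between-group ratios or differences with 95% CIs.

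**The concern.** A sensitivity analysis is informative only if it changes the subjects, the estimator or an assumption. For the OPA booster ratio this one changes none of them. Two identical ratios in the study report could be read as showing that the pandemic-related replacement did not matter, although nothing was tested.

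The second part concerns IgG as well as OPA. Objective 7 asks how the PNEUMOSIL booster response compares with those of Prevenar 13 and Synflorix. The plan supplies the three within-arm ratios but not the contrast between them, so a reader who wants the stated comparison has to construct it.

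**Working it through.** **The two analyses side by side**

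| | Main booster ratio (SAP 5.1 item 4, Protocol 12.7.2) | Check (SAP 5.3.7) |
|---|---|---|
| Subjects | results at both V4 and V6 | results at both V4 and V6 |
| Estimator | antilog of mean within-subject log10 difference | same analysis repeated |
| Replacement without a V4 titer | out | out |
| Replacement with a V4 titer | in | in |

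The two samples coincide in either case. A simulation confirms it: 50 V4 subjects, 5, 15 or 25 replaced, CV 2.11, correlation 0.5, and replacements 0.5 ln units higher at V6 (counts, correlation and shift assumed). The largest difference between main and check was 0.0. An all-available ratio (all V6 over all V4) differed from the paired ratio by factors of 1.05, 1.16 and 1.28, close to exp(0.5k/50) for k replaced. Different data can therefore show an effect of replacement; the planned repeat cannot.

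**Where the check can move.** The V4 GMT could change, but the check compares completers with a total that contains them. If the k drop-outs have a V4 GMT lower by a factor d, and replacements have no V4 titer, restricted/all = d^(k/50). For k = 10 or 15 and d = 1.5 or 2 (assumed):
- d = 1.5: 1.08 (k = 10), 1.13 (k = 15)
- d = 2: 1.15 (k = 10), 1.23 (k = 15)

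**The plan's own precision figures.** With s = sqrt(ln(1+CV²)), SAP 3.2 gives:
- OPA: CV 2.11, s = 1.302, 50 less 10% = 45 per arm. GMT: exp(±2.015 × 1.302/√45) = 0.68 to 1.48. GMT ratio: exp(±1.987 × 1.302 × √(2/45)) = 0.58 to 1.73.
- IgG: CV 1.5, s = 1.086, 220 less 10% = 198 per arm. GMC 0.86 to 1.16; GMC ratio 0.81 to 1.24.

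All match the SAP.

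**The missing contrast.** For the ratio of fold-rises with m pairs per arm, the expected 95% CI around 1 is exp(±t(2m−2) × s × √(2(1−ρ)) × √(2/m)), with equal CVs at V4 and V6. SAP 3.2.3 calls the V4-V6 correlation ρ positive but gives no value, so 0.5 and 0.3 are assumed.

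| | ρ = 0.5 | ρ = 0.3 |
|---|---|---|
| OPA, 45 pairs | 0.58–1.73 | 0.52–1.91 |
| OPA, 35 pairs | 0.54–1.86 | 0.48–2.09 |
| IgG, 198 pairs | 0.81–1.24 | 0.78–1.29 |

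The 35-pair row shows what happens if 15 of 50 are replaced by subjects without a V4 titer. The SAP 3.5 top-up rule aims at 45 per arm at each timepoint, which is not the same as 45 pairs.

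**What a direct look at drop-outs could show.** V4 GMT ratio, subjects with versus without V6 data, pooled over three arms and adjusted for arm: exp(±1.976 × 1.302 × √(1/a+1/b)). This gives 0.59 to 1.69 for 120 versus 30 subjects and 0.63 to 1.58 for 105 versus 45 (counts assumed). Only large differences would be visible.

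**The case against.** **The check may be meant for an unpaired main analysis.** Read alone, 5.3.7 speaks of a ratio of within-group GMCs and GMTs, and it adds the check because replacements joined the OPA set. That fits all V6 over all V4, and then the restriction would change the sample. This stands as a reading of 5.3.7, but it conflicts with SAP 5.1 item 4 and with Protocol 12.7.2. One of the two needs correcting either way.

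**The study is descriptive, and the SAP follows the protocol.** Protocol 12.7.2 also specifies only within-group CIs for Objective 7. Between-group ratios are planned separately at V4 and V6. The arms are independent, so a reader can rebuild the contrast: at 45 pairs and ρ = 0.5, combining two within-arm log half-widths of 0.391 gives √2 × 0.391 = 0.553, or 0.575 to 1.739. Protocol 1.8.2 also counts unequal starting levels among its reasons for caution about fold-rise. All of this is fair. It makes the gap modest, and it argues for showing the contrast beside the V4 ratios. It does not explain why only this comparative objective lacks an estimate.

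**A reader might infer that the within-group CI is computed wrongly**, because item 4 refers to item 3, the between-group method. The documents do not support that. The natural reading is that the CI limits of the paired mean are back-transformed, and SAP 3.2.3 relies on within-subject correlation for booster-effect precision. No wider interval follows.

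**The replacement details are editorial.** SAP 3.1 names V5 or V6 as the trigger for replacement and SAP 3.5 names V5. Neither says outright whether replacements have V4 OPA results. These need clarification, but the duplication does not depend on them.

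**Conclusion.** The point holds for the OPA booster ratio. Under SAP 5.1 item 4 and Protocol 12.7.2, the 5.3.7 check must reproduce the main result exactly. This follows from the text and needs no assumption about how many subjects were replaced or how they differ. Only the separate V4 and V6 GMTs could change, by a factor of 1.08 to 1.23 at V4 under the assumed drop-out patterns.

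The missing between-group CI also holds, for IgG and OPA. It is a gap against the wording of Objective 7, not an error of calculation. The intervals above rest on the SAP's maximum CVs and on assumed correlations.

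Two stronger readings are not supported. A reader might infer that replacement biases Objective 7. The redundant table biases nothing, and the SAP attributes the losses to pandemic visit schedules, with no sign that they depend on titer. A reader might also extend the problem to IgG, but SAP 3.1 has IgG measured in all subjects with evaluable specimens, so replacement does not arise there. No primary endpoint, sample size or safety conclusion is affected.

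**What to change.** 1. In SAP 5.3.7, name the paired V6/V4 ratio of 5.1 item 4 as the main analysis, and report the number of OPA pairs per arm. In the same edit, align the replacement trigger in 3.1 and 3.5 and state whether replacements have V4 OPA results.
2. Replace the duplicate check with an analysis of all available V4 and V6 OPA data: either the all-available GMT ratio, or a log-linear mixed model by arm and visit. Label it as sensitivity only, and note two limits.
   - It brings in V4-only subjects, who are outside the Primary PP_IMM Population.
   - Missing at random (SAP 3.13.1) may not hold exactly for replacements selected because they completed later visits. In one assumed case (15 of 50 replaced, drop-outs' V4 GMT half that of completers, ρ = 0.3, replacements with V6 only), the true fold-rise exceeds the paired one by 2^(0.7 × 15/50) = 1.157, and the model gives 1.173. The error is small but should be disclosed.
3. Tabulate V4 OPA GMTs for subjects with and without V6 data, pooled over arms with adjustment for arm.
4. Add the ratio of fold-rises, PNEUMOSIL versus each comparator, for IgG and OPA, with descriptive 95% CIs from a two-sample comparison of within-subject log10 differences. Show it beside the V4 GMC and GMT ratios.

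The cost is SAP wording, one sensitivity analysis and two small tables, with no new data. The downsides are a sensitivity population that differs from the main one and an imprecise V4 table.
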